##### 3-Month (90 ± 14 days), 6-Month (183 ± 21 days), 12-Month (365 ± 21 days) Follow-up

- Complete QOL (EQ-5D-5L & AFEQT)
- 12-lead ECG
- 24-hour Holter monitor at the 12-Month Follow-up
- Document adverse events and protocol deviations.
- Document AAD and anti-coagulant usage.
- If there are symptoms present that suggest pulmonary vein stenosis (e.g. shortness of breath, cough, and hemoptysis), complete CT or MRI imaging of pulmonary veins.
- Provide subject a trans telephonic monitor to record monthly heart rhythm and symptomatic episodes during follow up from 3 to 12 months.

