#### 5.3.5 Re-ablation Procedure and Anti-Arrhythmic Drug Usage

Subjects may be re-treated with ablation up to two times during the 90-day blanking period between days 31 and 80 after the index procedure. Re-ablation cannot be performed within 30 days of the latest ablation procedure. Re-treatment during this interval will not constitute a treatment failure and must be performed with the TactiCath SE catheter. Re-ablation per standard of care after the blanking period may be performed if recurrence is detected using any commercially available catheter. This will be counted as a treatment failure.

During the blanking period, it is recommended that any current antiarrhythmic medication be continued following the ablation procedure. Current AADs should be withdrawn 4-6 weeks after ablation, unless clinically contraindicated to assess for recurrence of symptoms and the necessity for re-ablation during the blanking period.

If documented symptomatic AF recurs during the 3-month blanking period and the patient requires antiarrhythmic drug therapy, a previously ineffective but tolerated antiarrhythmic drug may be re-initiated to allow for the assessment of its effectiveness when combined with ablation.

All Class I and Class III AADs will be discontinued at the end of the blanking period. Beta-blockers, calcium channel blockers or digitalis may be used during the 9-month chronic effectiveness assessment period if prescribed for reasons unrelated to arrhythmia management. Subjects are encouraged to continue their use through the end of the study unless it is determined to be unnecessary or detrimental by the investigator. Subjects who experience a recurrence of symptomatic PAF after the blanking period (treatment failure) should retry a previously failed AAD before a new medication is prescribed to evaluate the effectiveness of combined ablation and drug therapy.

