**Table 2 List of all clinical investigation specific tests and activities**

Study Activity	Enrollment/ Baseline	Procedure (within 14 days of consent)	Pre- Discharge	7-Day Visit (± 2 days)	30-Day Visit (± 7 days)	3-month Visit (± 14 days)	6-month Visit (± 21 days)	12-month Visit (± 21 days)
Eligibility Check	X							
Informed Consent Process	X							
Demographics / Medical History	X							
Physical Examination (including neurological assessment)	X		X	X				
NIHSS	X		X	X				
Diffusion-weighted MRI - Brain	(X)		(X)	(X)				
CT or MRI of pulmonary veins				(X)	(X)		(X)	(X)
Urine pregnancy test	(X)							
NYHA	X							
Record Antiarrhythmic / Anti- coagulant Medication	X		X	X	X	X	X	X
Confirm absence of thrombus (per standard of care)**	X	(X)						
Ablation procedure		X						
Trans thoracic echocardiogram		X*						
Trans telephonic monitoring***						X	X	X
12-Lead ECG	X				X	X	X	X
24-hour Holter-monitoring								
QOL (EQ-5D-5L & AFEQT)	X					X	X	X
Adverse Events	(X)	(X)	(X)	(X)	(X)	(X)	(X)	(X)
Deviation	(X)	(X)	(X)	(X)	(X)	(X)	(X)	(X)
Withdrawal	(X)	(X)	(X)	(X)	(X)	(X)	(X)	(X)
Health Care Utilization				(X)	(X)	(X)	(X)	(X)

(X) if applicable

\*Recommended post procedure to exclude pericardial effusion.

\*\*Must be done within one day of procedure (day of or day prior to).

\*\*\*Collected monthly and whenever symptoms are present from 3 to 12 months post ablation procedure.

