#### 6.1.7 Descriptive Endpoint #5

Descriptive endpoint #5 is one-year success, defined as freedom from symptomatic AF/AFL/AT lasting at least 30 seconds without a new Class I or III AAD or a higher dosage of pre-existing AAD as assessed from the end of the 3-month blanking period to 12 months following the ablation procedure.

A full 10-second 12-lead ECG recording of arrhythmia may be substituted for a 30-second recording unless there is evidence that the recorded arrhythmia is short-lived and less than 30 seconds.

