#### Blanking Period

The blanking period is the 90 days immediately following the index ablation procedure. During this time, recurrences of arrhythmias are not counted towards the trial effectiveness end point.

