### 6.5.2 Analysis population

The analysis population for this endpoint will include all enrolled subjects who have also had the TactiCath SE inserted into their vasculature and who have completed their 1-year visit or crossed the 1-year visit window without the visit but with an event as defined above for the descriptive endpoint #5.

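### The rhythm recorder is first supplied at the 3-month visit (day 76 to 104), but descriptive endpoints #5 and #6 count from day 91, so some unmonitored time is scored as event-free; the upward bias is small

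*Protocol*

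**What the plan says.** - **Supply of the recorder.** Protocol 5.3.4, under the heading "3-Month (90 ± 14 days), 6-Month (183 ± 21 days), 12-Month (365 ± 21 days) Follow-up", lists: "Provide subject a trans telephonic monitor to record monthly heart rhythm and symptomatic episodes during follow up from 3 to 12 months". The 30-day visit lists no TTM, and Table 2 marks TTM only at the 3-, 6- and 12-month visits. The Table 2 footnote gives the intended collection: "Collected monthly and whenever symptoms are present from 3 to 12 months post ablation procedure".
- **Start of counting.** Protocol Appendix B: "The blanking period is the 90 days immediately following the index ablation procedure". Endpoint #5 (Protocol 6.1.7) is judged "as assessed from the end of the 3-month blanking period to 12 months following the ablation procedure", and endpoint #6 (Protocol 6.1.8) uses the same interval. Protocol 5.3.5 calls it a "9-month chronic effectiveness assessment period".
- **Scoring.** The numerator for both endpoints is subjects without a failure (Protocol 6.1.7.1 and 6.1.8.1; SAP 6.5.1 and 6.6.1). The denominator is treated subjects "who have completed their 1-year visit or crossed the 1-year visit window without the visit but with an event" (SAP 6.5.2, with the same condition in SAP 6.6.2). Neither asks for the 3-month visit or for any TTM recording.
- **Missed visits.** Under Protocol 5.7 one missed visit does not by itself make a subject lost to follow-up; at least two failed telephone calls are also needed. A reachable subject who skips the 3-month visit stays in the trial.

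**The concern.** The TTM is the only rhythm recorder scheduled between visits. The other core-lab sources in Protocol 5.9 are the 12-lead ECG, scheduled at visits, and the 24-hour Holter, which 5.3.4 places at 12 months. Paroxysmal AF, as Appendix B defines it, ends within 7 days, so an episode can be over before the next visit ECG.

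A subject without a recorder can therefore have an undocumented recurrence in counted time and still be scored a success. This error runs one way: it can only raise the success rates. The same scoring rule credits a subject who holds a recorder and never transmits. The reported rates and their exact confidence intervals would not show how much of the period was actually monitored. At stake is the accuracy of the trial's only one-year rhythm results.

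**Working it through.** **Inputs from the documents**
- 3-month visit: 90 ± 14 = day 76 to 104 (29 possible days).
- 6-month visit: 183 ± 21 = day 162 to 204.
- Counting: day 91 (after 90 days of blanking) to day 365, taken as 12 months.

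**The plan's own figure.** 365 − 91 + 1 = 275 days, and 275 / 30.4375 = 9.03 months. This reproduces the stated 9-month period.

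**Step 1: 3-month visit attended.** Gap in full days = visit day − 91, or 0 if negative.
- Day 76 to 91 (16 of 29 days): no gap.
- Day 92 to 104 (13 of 29 days): gap of 1 to 13 days. The largest is 13 / 275 = 4.7%.
- Mean gap if visits are spread evenly (assumption): (1 + 2 + … + 13) / 29 = 91 / 29 = 3.1 days.

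**Step 2: 3-month visit missed, recorder supplied at the 6-month visit.**
- Day 162: 162 − 91 = 71 days, 26% of 275.
- Day 183: 92 days, 33%.
- Day 204: 113 days, 41%.

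These subjects also miss the 3-month ECG, so no rhythm recording is scheduled for them from day 91 until the 6-month visit.

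**Step 3: share of such subjects with a recurrence in the gap.** The documents give no recurrence rate. Assume a nine-month rate p of 20, 30 or 40% and a constant hazard, so share = 1 − (1 − p)^(gap/275).

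| Gap | p = 20% | p = 30% | p = 40% |
|---|---|---|---|
| 13 days | 1.05% | 1.67% | 2.39% |
| 71 days | 5.60% | 8.80% | 12.36% |
| 92 days | 7.19% | 11.2% | 15.71% |
| 113 days | 8.76% | 13.63% | 18.93% |

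**Step 4: effect on the whole cohort.** Let m be the share who miss the 3-month visit (assumed 0, 5 or 10%). Attended visits are spread evenly over day 76 to 104, and missed ones are made good on day 183. Effect = (1 − m) × mean share over attended visits + m × share for 92 days, in percentage points:

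| m | p = 20% | p = 30% | p = 40% |
|---|---|---|---|
| 0% | 0.25 | 0.40 | 0.58 |
| 5% | 0.60 | 0.95 | 1.33 |
| 10% | 0.95 | 1.49 | 2.09 |

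If every missed subject were seen only on day 204, the last cell would become 0.9 × 0.58 + 0.1 × 18.93 = 2.4.

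Within these assumptions each figure is an upper limit: it treats every recurrence in the gap as a missed failure, although some will be documented by another route or followed by a recorded one. The figures cover the supply gap only. Failure to transmit cannot be sized, because the documents give no transmission rate.

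**The case against.** The best case against acting is that the gap is minor and the endpoints carry no test. Most of this stands.

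- **Small in-window gap.** It is under two weeks, shorter than one monthly TTM interval, so the loss is mainly of symptom-triggered recordings. More than half of the permitted visit days leave no gap.
- **Other routes to failure.** A reader might infer that no recorder means no detection. The documents do not support that. A full 10-second 12-lead ECG can stand in for a 30-second recording, and the definitions do not confine it to scheduled visits. A new Class I or III drug or a higher dose of an existing one (#5), any such drug (#6), or re-ablation after blanking also counts. The late 3-month visit itself includes an ECG and a drug record.
- **Drug withdrawal.** From "All Class I and Class III AADs will be discontinued at the end of the blanking period" a reader might infer that the gap falls in the first weeks off antiarrhythmic drugs. The same section (5.3.5) has current drugs withdrawn 4 to 6 weeks after ablation unless contraindicated. The inference fits only subjects still on such a drug, or restarted on one, when blanking ends.
- **Supply by another route.** The Table 2 footnote shows that coverage from 3 months is intended, and nothing forbids shipping the recorder. Equally, nothing provides for it, so the missed-visit gap is what follows from the plan as written, not something the plan states.
- **Limited consequence.** Endpoints #5 and #6 are descriptive, have no success criterion and are not meant to support labeling claims.

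The objection does not answer the scoring rule. Neither document sets a minimum of monitoring, censors unmonitored time or says what happens to the recorder when the 3-month visit is missed.

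**Conclusion.** The point holds as a small, one-directional bias in two descriptive rates. The largest in-window gap is 13 days. The missed-visit gap, 71 to 113 days, matters more for the individual subject but depends on how often it happens. Over the cohort the supply gap is worth at most about 0.3 to 2.1 percentage points. That range rests on assumed recurrence of 20 to 40%, a constant hazard, evenly spread visits, and 0 to 10% missed 3-month visits made good on day 183. If recurrences cluster soon after blanking, the share falling in the gap would be larger.

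A reader might go further and infer that the trial's success claim is in doubt. It is not: success rests on the 7- and 30-day safety endpoint and acute procedural success (Protocol 6.6, SAP 5.7), which use no TTM data. The change is worth making because it is cheap and because the planned outputs would not reveal how fully subjects were monitored.

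**What to change.** - **Protocol 5.3.4 and Table 2.** Have the TTM in the subject's hands by day 90, either given at the existing 30-day visit or shipped, with recordings starting on day 91. State that this applies equally to subjects who miss the 3-month visit.
- **SAP 6.5 and 6.6.** Report the number of TTM recordings received per subject. Add a supportive analysis, with the denominator unchanged, in which an event-free subject counts as a success only if a prespecified minimum of monthly recordings was received. The sponsor should set that minimum before reviewing the data; the documents offer no basis for a particular value.

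The cost is some extra recorder time per subject, one extra table, and a supportive success rate that may be lower than the main one. No new visit or procedure is needed. If follow-up is too far along for earlier supply to help, the SAP additions still can, because they use recordings already collected.

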#### 5.3.5 Re-ablation Procedure and Anti-Arrhythmic Drug Usage

Subjects may be re-treated with ablation up to two times during the 90-day blanking period between days 31 and 80 after the index procedure. Re-ablation cannot be performed within 30 days of the latest ablation procedure. Re-treatment during this interval will not constitute a treatment failure and must be performed with the TactiCath SE catheter. Re-ablation per standard of care after the blanking period may be performed if recurrence is detected using any commercially available catheter. This will be counted as a treatment failure.

During the blanking period, it is recommended that any current antiarrhythmic medication be continued following the ablation procedure. Current AADs should be withdrawn 4-6 weeks after ablation, unless clinically contraindicated to assess for recurrence of symptoms and the necessity for re-ablation during the blanking period.

If documented symptomatic AF recurs during the 3-month blanking period and the patient requires antiarrhythmic drug therapy, a previously ineffective but tolerated antiarrhythmic drug may be re-initiated to allow for the assessment of its effectiveness when combined with ablation.

All Class I and Class III AADs will be discontinued at the end of the blanking period. Beta-blockers, calcium channel blockers or digitalis may be used during the 9-month chronic effectiveness assessment period if prescribed for reasons unrelated to arrhythmia management. Subjects are encouraged to continue their use through the end of the study unless it is determined to be unnecessary or detrimental by the investigator. Subjects who experience a recurrence of symptomatic PAF after the blanking period (treatment failure) should retry a previously failed AAD before a new medication is prescribed to evaluate the effectiveness of combined ablation and drug therapy.

#### **5.4 Investigation Specific Tests and Activities**

The following table summarizes the investigation specific tests and activities.

Test/Activity	Frequency	Responsible Party	Notes
ECG	Baseline and periodic	Investigator	Standard 12-lead ECG
Vital Signs	Baseline and periodic	Investigator	Heart rate, blood pressure, temperature, oxygen saturation
ECG Holter	During treatment	Investigator	24-hour monitoring
Exercise Test	Baseline and periodic	Investigator	Standard treadmill test
Lab Tests	Baseline and periodic	Investigator	Electrolytes, renal function, liver function, etc.
Drug Levels	Baseline and periodic	Investigator	Thrombolytic, antiarrhythmic, etc.
Ablation Procedure	Once	Investigator	Radiofrequency catheter ablation
ECG Mapping	Baseline and periodic	Investigator	Electroanatomical mapping
ECG Implantation	Once	Investigator	Implantation of Class I/III AAD
ECG Follow-up	Baseline and periodic	Investigator	ECG monitoring post-procedure
ECG Implantation	Once	Investigator	Implantation of Class II AAD
ECG Follow-up	Baseline and periodic	Investigator	ECG monitoring post-procedure

**Abbott**

Study Document No: SJM-CIP-10216 Ver. E  
Study Name: TactiSense IDE

Clinical Investigation Plan

**Table 2 List of all clinical investigation specific tests and activities**

Study Activity	Enrollment/ Baseline	Procedure (within 14 days of consent)	Pre- Discharge	7-Day Visit (± 2 days)	30-Day Visit (± 7 days)	3-month Visit (± 14 days)	6-month Visit (± 21 days)	12-month Visit (± 21 days)
Eligibility Check	X							
Informed Consent Process	X							
Demographics / Medical History	X							
Physical Examination (including neurological assessment)	X		X	X				
NIHSS	X		X	X				
Diffusion-weighted MRI - Brain	(X)		(X)	(X)				
CT or MRI of pulmonary veins				(X)	(X)		(X)	(X)
Urine pregnancy test	(X)							
NYHA	X							
Record Antiarrhythmic / Anti- coagulant Medication	X		X	X	X	X	X	X
Confirm absence of thrombus (per standard of care)**	X	(X)						
Ablation procedure		X						
Trans thoracic echocardiogram		X*						
Trans telephonic monitoring***						X	X	X
12-Lead ECG	X				X	X	X	X
24-hour Holter-monitoring								
QOL (EQ-5D-5L & AFEQT)	X					X	X	X
Adverse Events	(X)	(X)	(X)	(X)	(X)	(X)	(X)	(X)
Deviation	(X)	(X)	(X)	(X)	(X)	(X)	(X)	(X)
Withdrawal	(X)	(X)	(X)	(X)	(X)	(X)	(X)	(X)
Health Care Utilization				(X)	(X)	(X)	(X)	(X)

(X) if applicable

\*Recommended post procedure to exclude pericardial effusion.

\*\*Must be done within one day of procedure (day of or day prior to).

\*\*\*Collected monthly and whenever symptoms are present from 3 to 12 months post ablation procedure.

### 5.5 Description of Activities Performed by Sponsor Representatives

Trained Sponsor personnel may provide technical expertise and technical guidance on the use of the device. While Sponsor representatives may perform these activities, the Principal Investigator remains responsible for ensuring all clinical investigation data is collected as required per the CIP.

### 5.6 Subject Study Completion

Subject participation in the clinical investigation will conclude upon completion of the 12-Month visit. Upon completion of subject participation in the clinical investigation, the subject will return to standard of care.

### 5.7 Subject Withdrawal

Subjects must be informed about their right to withdraw from the clinical investigation at any time and for any reason without sanction, penalty or loss of benefits to which the subject is otherwise entitled. Withdrawal from the clinical investigation will not jeopardize their future medical care or relationship with the investigator. Subjects will be requested to specify the reason for the request to withdraw. The investigator must make all reasonable efforts to retain the subject in the clinical investigation until completion of the clinical investigation.

A subject will be considered 'Lost to Follow-up' after one missed visit(s) and a minimum of two unsuccessful phone calls from investigational site personnel to the subject or subject's contact to schedule the next follow-up visit. These two phone calls must be documented in the subject's hospital records. If the subject is deemed lost to follow-up, a letter should be sent to the subject's last known address or to the subject's general practitioner (GP) and a copy of the letter must be maintained in the subject's hospital records.

### 5.8 Clinical Events Committee (CEC)

A CEC will be responsible for providing an independent review and adjudication of adverse events. The CEC will make the final determination whether or not an adverse event meets the criteria for the primary endpoint. The primary function, responsibilities and membership of the CEC will be described in detail in a CEC charter.

### 5.9 Core Lab

A core lab will be used for the collection, interpretation, and collation of data collected from the following procedures:

- Trans telephonic monitoring (TTM)
- 24-hour Holter monitoring
- 12-lead ECG

The core lab will provide independent review of this data by appropriately trained personnel using standardized procedures to interpret TTM, 24-hour holter and 12-lead ECG tracings and adjudicate atrial arrhythmias. Findings will be communicated to the investigator and the sponsor.

## 6 Statistical Considerations

The following section describes the statistical methods for the clinical investigation and justification of the design. Additional details on statistical analyses, including sensitivity analyses, poolability analyses, subgroup analyses and analysis of descriptive endpoint(s) are maintained in a separate Statistical Analysis Plan (SAP).

### 6.1 Hypotheses

There are two primary endpoints for this study and ten types of descriptive endpoints. Both the primary endpoints must be met for trial success.

### 6.1.1 Primary Safety Endpoint Hypothesis

The performance goal is set at 16.2% based on experience with the TactiCath ablation catheter (a prior generation of the TactiCath SE catheter, see below for further detail). The hypothesis is formally expressed as:

$$H_0: P \geq 16.2\%$$

$$H_a: P < 16.2\%$$

where P is the percentage of subjects with a primary safety endpoint event. The hypothesis will be tested based on a one-sided exact test of binomial proportions at the one-sided 0.05 alpha level. Rejection of the null hypothesis will indicate study success. The performance goal of 16.2% is set to be equal to that for previous generations of the TactiCath catheter.

#### 6.1.1.1 Analysis Methodology

The primary safety endpoint event rate will be calculated based on the number of subjects experiencing a primary safety endpoint divided by the total number of subjects in the analysis population. Relatedness of the event to the catheter and to the procedure will be determined by the CEC. The null hypothesis will be rejected if the upper bound of the one-sided 95% confidence interval for the proportion of subjects with a primary safety endpoint is less than 16.2%. Subjects without an event that are lost to follow up without a visit at or beyond their 30-day follow up visit window will be excluded from this analysis.

[REDACTED]

[REDACTED]

[REDACTED]

[REDACTED]

[REDACTED]

[REDACTED]

### 6.1.1.3 Analysis Population

The analysis population for this endpoint will include all enrolled subjects who have also had the TactiCath SE inserted into their vasculature, and either had an event or completed a visit at or beyond their 30-day follow up visit window. Subjects without an event that are lost to follow up without a visit at or beyond their 30-day follow up visit window will be excluded from this analysis.

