#### 4.3.1 Primary Safety Endpoint

The primary safety endpoint is the rate of device or procedure-related serious adverse events occurring within 7 days of the index procedure. SAEs related solely to arrhythmia recurrence (without coexisting conditions such as thromboembolism, worsening heart failure, etc.) will not be considered primary safety endpoint events. The SAEs that will be included in this endpoint are:

- Atrial-esophageal fistula
- AV block
- Cardiac perforation/ Tamponade
- Death
- Diaphragmatic paralysis
- Gastroparesis
- Hospitalization
- Myocardial Infarction
- Pericarditis
- Pneumothorax
- Pulmonary edema
- Pulmonary vein stenosis
- Stroke
- Thromboembolism
- Transient ischemic attack
- Vascular access complication

These events must meet the criteria listed in Appendix C to be included in the primary endpoint as adjudicated by the clinical events committee (CEC). Atrial-esophageal fistula, cardiac perforation/tamponade, and pulmonary vein stenosis that occur >7 days post procedure through 30 days will also contribute to the primary endpoint.

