### 5.1.2 Analysis Methodology

The primary safety endpoint event rate will be calculated based on the number of subjects experiencing a primary safety endpoint divided by the total number of subjects in the analysis population. The null hypothesis will be rejected if the upper bound of the one-sided 95% exact binomial confidence interval for the proportion of subjects with the primary safety endpoint is less than 0.162. Subjects who terminate the study prematurely without experiencing any primary safety endpoint events will be excluded.

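### A treated subject who dies on day 8 or later, before a 30-day visit and without a counted event, is dropped from the primary safety denominator although the outcome is known

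*Protocol*

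**What the plan says.** **Endpoint.** CIP 4.3.1: "The primary safety endpoint is the rate of device or procedure-related serious adverse events occurring within 7 days of the index procedure". Death is on the list of qualifying events. After day 7 the list shrinks to three: "Atrial-esophageal fistula, cardiac perforation/tamponade, and pulmonary vein stenosis that occur >7 days post procedure through 30 days will also contribute to the primary endpoint". SAP 4.1 agrees.

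**Population.** CIP 6.1.1.3 and SAP 5.1.4 require insertion of the catheter and that the subject "either had an event or completed a visit at or beyond their 30-day follow up visit window". CIP 4.1 ties the term event to section 4.3.1 when it sets the reporting trigger.

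**Exclusions.** CIP 6.1.1.3 adds: "Subjects without an event that are lost to follow up without a visit at or beyond their 30-day follow up visit window will be excluded". CIP 5.7 defines loss to follow-up by one missed visit plus at least two failed calls; death is not part of that definition. SAP 5.1.2 is broader: "Subjects who terminate the study prematurely without experiencing any primary safety endpoint events will be excluded". Neither document says whether death is a premature termination.

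**Test.** SAP 5.1.2 gives the condition for rejecting the null hypothesis: "upper bound of the one-sided 95% exact binomial confidence interval for the proportion of subjects with the primary safety endpoint is less than 0.162".

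**Related rules.** The tipping-point analysis in SAP 5.1.6 covers early terminators without a primary event. For descriptive endpoints 3 and 4 (CIP 6.1.5 and 6.1.6, SAP 6.3 and 6.4) early terminators without events stay in the denominator and count as having none. The trigger of at least 140 subjects in CIP 4.1 and SAP 3 has three categories: event, 30-day visit, lost to follow-up.

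**The concern.** A subject who dies on day 15 without a counted event can neither attend the 30-day visit nor later become an event. That subject meets neither arm of the population rule, and no sentence brings the subject back. Yet nothing is missing: day-7 status is known, the three late event types can be adjudicated up to death, and none can occur afterwards. The rule treats a complete outcome as missing data.

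At stake is the denominator of the endpoint that, with acute effectiveness, decides trial success. Because the CIP names only loss to follow-up and the SAP names premature termination, two analysts could also disagree about whether such a death belongs in the tipping-point set. Descriptive endpoints 3 and 4 take the opposite approach for early terminators, and the visible text gives no reason for the difference.

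**Working it through.** The sample-size sections are redacted, so there is no planned event rate or power to reproduce. The checks are a reading of the rule and a calculation of its effect.

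**1. Inputs.** Performance goal 16.2% and one-sided exact test at 0.05 (CIP 6.1.1); rejection rule on the exact upper bound (SAP 5.1.2); analysis at 140 subjects with data (CIP 6.5, SAP 5.6); 156 enrolled (CIP 4.1); 30-day visit on days 23 to 37 (CIP 5.3.4). The event counts below are illustrative.

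**2. Formula.** For x events in n subjects, the one-sided 95% Clopper-Pearson upper bound is U(x, n) = the 0.95 quantile of Beta(x + 1, n − x). The goal is met if U < 16.2%.

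**3. Largest passing event count.**

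| n | maximum x |
|---|---|
| 132–138 | 14 |
| 139–145 | 15 |
| 146–152 | 16 |

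**4. Effect of dropping against keeping as event-free**, assuming 140 treated subjects including the deaths:

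| Deaths | Counted events | Dropped (as written) | Kept, event-free |
|---|---|---|---|
| 1 | 15 | 15/139: 16.13%, pass | 15/140: 16.02%, pass |
| 2 | 15 | 15/138: 16.24%, fail | 15/140: 16.02%, pass |
| 2 | 14 | 14/138: 15.40%, pass | 14/140: 15.19%, pass |

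Each dropped death raises the bound by about 0.1 point (16.13 − 16.02 = 0.11). The result changes only in the second row, where the denominator falls from the 139–145 band into the 132–138 band.

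**5. Dependence on the timing rule.** If deaths do not count towards 140 and 140 other subjects have data (CIP 6.5), two deaths compare 15/140 = 16.02% with 15/142 = 15.80%: both pass. With 16 events, 16/140 = 16.84% and 16/142 = 16.61% both fail; six deaths would be needed to pass (16/146 = 16.17%). The trigger in CIP 4.1, however, counts subjects lost to follow-up, whom the analysis then excludes. With 138 assessable and two lost (138 + 2 = 140), a single death outside the trigger gives 15/138 = 16.24% (fail) as written and 15/139 = 16.13% (pass) if kept.

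**6. How often.** CIP section 2 cites 3% annual mortality in anticoagulated AF patients. Assuming it applies here, 140 subjects over about 22 days give 140 × 0.03 × 22/365 = 0.25 expected deaths, and a Poisson chance of two or more of 1 − e^(−0.253) × 1.253 ≈ 3%. At half that rate the chance is about 0.7%, and at double about 9%. Exactly 15 events in 138 has at most about an 11% chance, so at the 3% rate the two-death reversal has a joint chance of about 0.027 × 0.11 ≈ 0.3%, if the two are independent.

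**7. Sensitivity row.** With 15 counted events and one related death on days 8–30, counting the death as an event gives 16/140 = 16.84%, above the goal. That is about 0.8 point over 15/140 (16.84 − 16.02 = 0.82). It measures a different endpoint definition, not the population rule.

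**The case against.** The strongest case is that this is a wording gap of little consequence. Dropping such deaths is conservative, and the proposed primary rule only makes success easier. One death does not change the result when 140 treated subjects include it. The two-death reversal needs exactly 15 events and disappears if the analysis waits for 140 other subjects with data. Such deaths should be few: CIP 4.4.2 excludes NYHA class III or IV, ejection fraction below 35% and patients unlikely to survive 12 months. If SAP 5.1.2 reaches deaths, SAP 5.1.6 uses the same term and already imputes them as events. Deaths also appear in the mortality summary (SAP 6.12), and related events through 30 days in descriptive endpoint 3.

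Most of this stands, and it sets the size of the point. It does not remove the gap. The tipping-point coverage depends on an unstated reading of death as termination, it imputes outcomes that are already known, and it leaves the primary test unchanged.

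A reader might infer that the population rule hides device-related deaths and so flatters the device. The documents do not support that. A related death on day 15 without a counted event is absent from the numerator because CIP 4.3.1 closes the general window at day 7; it would be absent under any population rule. Relative to keeping the subject as event-free, the rule raises the bound.

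**Conclusion.** The population rule gives a wrong denominator for a small, identifiable group: treated subjects who die on day 8 or later, before a 30-day visit and without a counted event. Their outcome is complete and they should stay in.

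The effect is about 0.1 percentage point on the upper bound per death, slightly against the device. Pass or fail changes only at a boundary, such as 15/138 (16.24%) against 15/139 (16.13%), and that should be rare. This rests on exact one-sided 95% bounds, on reading the term event as the endpoint in CIP 4.3.1, and on about 140 analysed subjects. The mortality rate used for frequency is an assumption.

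The 16.84% for 16/140 should not be read as the error in the current primary analysis. It arises only if a late related death counts as an event, which the endpoint definition does not do. The point merits correction because it is cheap and concerns how deaths are handled in a safety endpoint, not because it is likely to decide the trial.

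**What to change.** 1. In CIP 6.1.1.3 and SAP 5.1.4, extend the population rule with: *or died before completing a 30-day visit*.
2. In SAP 5.1.2, exempt deaths from the exclusion of early terminators. State that subjects who die stay in as event-free unless they had a counted event. The CIP exclusion sentences name only loss to follow-up and need no change.
3. This takes these deaths out of the tipping-point set in SAP 5.1.6. Add one prespecified sensitivity row that counts every death through day 30 adjudicated by the CEC as device- or procedure-related as an event, reported against 16.2%.
4. Give deaths a category in the 140-subject trigger in CIP 4.1 and SAP 3.

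The cost is a few sentences and one extra row, with no new data and no change to the endpoint definition. The downside is that the row can look less favourable than the primary result, as with 16/140 = 16.84%.
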